Risks: Spirometry will be performed to determine the participants' pulmonary function. The risks of spirometry are minimal. The possible risks include precipitation of bronchospasm and light-headedness from repeated blowing attempts. Medical and nursing personnel and medications will be available at the study sites to treat and manage bronchospasm. Inhalation of a short acting beta-2 adrenergic agonist (albuterol) and a short-acting anti-cholinergic (ipratropium, Atrovent® HFA) will be used to assess reversibility. The possible risks of inhaled beta-2 adrenergic agonists include tachycardia and hand tremors. Ipratropium (Atrovent® HFA) is an anticholinergic bronchodilator that is FDA approved for the treatment of chronic bronchitis, emphysema and chronic obstructive pulmonary disease (COPD). Although ipratropium has not been FDA-approved for use in asthma, it is widely used for asthma, and an NIH Task Force ³² and US and International guidelines ³³ all recommend ipratropium in this dose for characterization of asthma. This is another test to measure improvement in spirometry but showing improvement with this test is not a screening requirement. Taking the 4 puffs of ipratropium (Atrovent® HFA) required for this test can cause adverse effects including headache, dry mouth, nausea, bronchitis, and shortness of breath. These side effects were reported in patients with COPD who took ipratropium for 12-weeks. Since participants will only take

ipratropium once, the likelihood of these side effects is much less. The safety of ipratropium in children is not known.

Benefits: Spirometry with assessment of reversibility to a short acting beta-2 adrenergic agonist and to ipratropium (Atrovent® HFA) will be used to determine if the participants meet the inclusion criteria for this study and to examine whether a differential response to beta-2 adrenergic agonists vs anti-cholinergics predicts response to ICS vs. LMA. Spirometry will be used during the study to monitor for asthma control and treatment failure.

The potential benefits justify the potential risks.

Methacholine inhalation challenge: Methacholine challenge will be used to assess airway hyper-responsiveness.

Risks: The major risk of methacholine challenge is the induction of severe bronchoconstriction. As a precaution, participants will not undergo methacholine challenge if their FEV1 is less than 55% of predicted or 1.0 liter. Medical and nursing personnel, medications and equipment will be available at the study sites to treat and manage any bronchoconstriction episodes.

Benefits: There are two benefits to this procedure. First, for the participants who do not demonstrate a 12% improvement in FEV1, a positive methacholine challenge would allow them to meet one of the inclusion criteria for this study. Second, the comparison of the methacholine PC₂₀ in eosinophil positive vs eosinophil negative participants will provide important characterization of these 2

phenotypes - which may be important in predicting or interpreting response to asthma treatments.

The potential benefits justify the potential risks.

Induced sputum: Sputum will be induced with hypertonic saline to collect an airway sample and to assess for airway inflammation.

Risks: Like any bronchoprovocation challenge, sputum induction can provoke bronchospasm and warrants close supervision during its performance.

Benefits: There are no direct benefits to the participant. This procedure will allow us to characterize participants as "eosinophilic" or "non-eosinophilic" and is a requirement for stratification prior to randomization.

The potential benefits justify the potential risks.

Exhaled Nitric Oxide: *Exhaled Nitric Oxide will be measured each time a participant undergoes sputum induction. This involves exhaling gently into a small, handheld device that measures FeNO.*

Risks: The risks of this maneuver are minimal. As with spirometry, it is possible that a participant could become lightheaded from blowing, but these are not forced maneuvers.

Benefits: There is no direct benefit to participants. This information provides an assessment of the amount of inflammation in the airways, which may relate to asthma control. This measurement is an exploratory outcome of the study, to be compared with sputum eosinophils.

The potential benefits justify the potential risks.

B. Risks of Study Design

Risks: Participants in the study have persistent symptomatic asthma and will not receive regular inhaled corticosteroids during the 4-6 week Run-In Period and during 2 of the 3 three-month-long double-blind Treatment Periods. (All participants will, however, receive inhaled corticosteroids if their asthma control deteriorates). In addition, we believe that the "eosinophil negative" participants will not respond to inhaled corticosteroid treatment. It is therefore likely that a significant number of participants will experience deterioration of asthma control during the study. For this reason, we have defined a Treatment Failure status that we believe is sufficiently conservative that participants whose asthma control deteriorates will be "rescued" before they develop an asthma exacerbation. This rescue algorithm was used successfully in the NHLBI-ACRN IMPACT study³ - a comparison of daily versus "as-needed" ICS for mild persistent asthma. Participants who meet treatment failure status during the Run-in will be treated according to a rescue algorithm and will continue in the study. If necessary, the run-in will be extended so that ≥ 3 weeks elapse after TF before randomization. Participants with ≥ 2 TFs during the Run-In will be excluded from the double-blind Treatment Period. To provide an additional level of safety, we have added additional exclusion criteria at the end of the Run-In that must be met before participants can be randomized. Finally, TF criteria will also be used throughout the treatment period - to ensure the safety of participants.

We have designed the study with frequent study visits and phone visits (every 3 weeks) to allow for close monitoring of asthma control. All participants will be given an electronic diary/peak flow device at entry into the Run-In, which will provide objective data for assessment of control. Participants who do not adhere to this monitoring on 75% of days will not be permitted to proceed to the double-blind Treatment Period.

Participants who experience an Asthma Exacerbation will be treated with prednisone and seen at the clinic after 3 days to ascertain the severity of the event and ensure appropriate treatment. As part of our "characterization of asthma exacerbations", they will be evaluated in person or by phone on days 3, 10, 14, and 21.

Benefits: Although we can guarantee no direct benefit for participants, it is possible that those individuals who are "eosinophil negative" and who we believe do not respond to ICS, may respond favorably to LMA.

With all of these safeguards in place, we believe we have designed a study where ***the potential benefits justify the potential risks.***

C. Risks and Benefits of Study Drugs

Inhaled Corticosteroid (ICS): ICS is the standard treatment for chronic persistent asthma.

Risks: The potential risks of ICS are well-known, and include oropharyngeal candidiasis, thinning of skin, osteoporosis, and cataracts. There is no reason to believe that the risk is greater in this patient population.

Benefits: We may learn that participants who are eosinophil negative do better with LMA than with ICS, which may allow them to minimize their potential risk in the future.

The potential benefits justify the potential risks.

Long-acting Muscarinic Antagonist (LMA): All participants will take an LMA (tiotropium RESPIMAT 5mcg QD) during 1 of 3 double-blind Treatment Periods.

Risks: In general, LMAs have a well-established safety profile in COPD. Tiotropium Respimat was approved for treatment of COPD in the US in September 2014, and for treatment of asthma in the US in September 2015. It is also approved in many other countries for treatment of chronic obstructive pulmonary disease (COPD). A different form of tiotropium (Spiriva® HandiHaler) has been approved and used in the US for the treatment of COPD since 2004.

Tiotropium Respimat has been tested in 3282 patients with COPD and 1634 adult and adolescent patients with asthma. The most commonly reported adverse reactions were pharyngitis, cough, dry mouth and sinusitis. Tiotropium should not be taken by patients with narrow angle glaucoma (high pressure in the eyes), prostatic hypertrophy (enlarged prostate), bladder-neck obstruction (difficulty in urination), or renal insufficiency (kidney disease). A few reports suggested the possibility that tiotropium Respimat might increase the risk of stroke, heart attack, and death in patients with COPD when compared with the FDA-approved tiotropium Handihaler formulation available for treatment. To clarify this question and to exclude a relation between treatment with tiotropium

Respimat and an increased rate of deaths, a large long-term study of 17,135 patients with COPD was conducted. Analysis of the data from the trial concluded that tiotropium Respimat had a safety profile similar to tiotropium HandiHaler in patients with COPD, and was not associated with an increased risk of death.

Participants with history of urinary retention, elevated intraocular pressure, and significant cardiovascular disease will be excluded from the study.

An IND has been obtained from the FDA (#121996) for the SIENA study.

Benefits: Tiotropium has been shown to be not inferior to salmeterol as add-on treatment in asthma, and in a small study tiotropium increased FEV1 in asthmatics with low sputum eosinophil counts. Because all patients do not respond to inhaled corticosteroids, and some appear to have adverse effects associated with their use, there is a need for additional controller medications which can be used when inhaled corticosteroid does not provide adequate asthma control. If tiotropium bromide is found to be effective when used in this manner, important benefits to asthma patients would be anticipated.

The potential benefits justify the potential risks.

X. ADVERSE EVENTS

A. Definition and reporting

Participants are at risk of developing adverse events during study enrollment. A clinical adverse event is any unintended worsening in the structure (signs) or function (symptoms) of the body, whether or not considered to be

study-related. This includes any side effect, injury, or sensitivity reaction, as well as any intercurrent event. A laboratory adverse event is any clinically-important worsening in a test variable which occurs during the course of the study, whether or not considered to be drug-related. An adverse event is deemed serious if it suggests a significant hazard, contraindication, side effect, or precaution. Serious adverse events include any experience that is fatal or life-threatening, is permanently disabling, requires or prolongs inpatient hospitalization, or is a congenital anomaly, cancer, or overdose.

Documentation of an adverse event will be recorded on the Clinical Adverse Event Report Form and will include the following information: Description of the condition, dates of condition, treatment of condition (medications, doses, dates), whether hospitalization or emergency treatment was required, treatment outcome, relationship of the adverse event to the study medication(s), and severity of the event.

B. Adverse Events Unrelated to Asthma

Adverse events due to concurrent illnesses other than asthma may be grounds for withdrawal if the illness is considered significant by the study investigator or if the participant is no longer able to effectively participate in the study. Participants experiencing minor intercurrent illnesses may continue in the study provided that the nature, severity, and duration of the illness are recorded and that any unscheduled medications required to treat the illness are also recorded. Examples of minor intercurrent illnesses include acute rhinitis, sinusitis, upper respiratory infections, urinary tract infections, and gastroenteritis.

Medications are allowed for treatment of these conditions in accordance with the judgment of the responsible study physician.

C. Adverse Events Related to Asthma: Treatment Failure and Asthma Exacerbation

Since participants have persistent symptomatic asthma and will not receive regular inhaled corticosteroids during the 4-6 week Run-In Period and during 2 of the 3 three-month long double-blind Treatment periods, we anticipate that asthma treatment failures will occur. Safety net procedures, including visits and frequent telephone contacts, are in place to identify participants who experience a treatment failure (a primary outcome) or asthma exacerbation during the study.

Between in-person study visits (as described above), participants will be contacted by telephone by the clinic coordinator to assure that they are continuing to participate appropriately in the study protocol, to answer any questions that may arise, and to assure that their asthma is under adequate control, as assessed by the participant. The coordinator will attempt to determine whether the participant is showing signs of treatment failure using specific criteria. If it is determined that the participant fulfills criteria for treatment failure, they will be advised to initiate high-dose ICS rescue treatment (i.e., mometasone 400-440 mcg BID, dose dependent on mometasone device randomized to at Visit 3 – See Appendix D x 10 days).

If, between phone contacts or in-person visits, an asthma exacerbation has occurred, the participant should contact the clinic coordinator and/or be

evaluated at the study site or the nearest medical emergency facility as quickly as possible (within 72 hours) for initiation of rescue prednisone. For both adults and children, the recommended prednisone dose for acute exacerbations is 2 mg/kg/day (maximum 60 mg) as a single morning dose for three days followed by 1 mg/kg/day (maximum 30 mg) as a single morning dose for 2 days. All administered doses will be rounded down to the nearest 5 mg in children. Phone visits will be conducted on days 10, 14, and 21, to monitor exacerbation recovery.

Definition of Treatment Failure:

The definition of TF is based on the Symptom-Based Action Plan that was used successfully in the ACRN IMPACT Study ³ and includes:

- Awakening from asthma three or more times in a two-week period or on two consecutive nights, or
- Using albuterol for relief of symptoms four or more times/day for two or more consecutive days, or
- Albuterol has been relieving symptoms for less than four hours after each treatment over a 12-hour period, or
- Using albuterol for relief of symptoms daily for seven days, and this use exceeds two times the weekly use of albuterol in the baseline period, or
- exercise induces unusual breathlessness.

Definition of Asthma Exacerbation:

Although all participants with an asthma exacerbation will also meet the criteria outlined for treatment failure above, asthma exacerbations are more severe episodes of acute worsening, defined by meeting criteria for treatment failure AND one or more of the following:

- Failure to respond within 48 hours to treatment failure rescue algorithm
- FEV1 <50% of baseline on 2 consecutive measurements
- FEV1 <40% of predicted on 2 consecutive measurements
- Use of \geq 16 puffs of "as needed" β -agonist per 24 hours for a period of 48 hours
- Experiencing an exacerbation of asthma in the opinion study investigator or personal physician
- Use of oral/parenteral corticosteroid due to asthma

D. Adjustments to Trial Medications and Rescue Algorithms during Treatment Failures and Asthma Exacerbations

Participants who develop treatment failure during the Run-In period or double-blind Treatment Period will be treated as described previously with high-dose ICS (i.e., mometasone 400-440 mcg BID, dose dependent on mometasone device randomized to at Visit 3 – See Appendix D x 10 days), and continue in the study. Participants who experience two treatment failures during the run-in period will not be allowed to participate in the study further. Participants who meet criteria for treatment failure during the double-blind Treatment Period will continue in the study. If the treatment failure occurs <3 weeks before the end of

a treatment period, that period will be extended so that ≥ 3 weeks will have elapsed before the participant crosses over to the next treatment arm (or has their final visit should this occur during the final treatment period). Participants who experience ≥ 2 Treatment Failure episodes or an Asthma Exacerbation during a treatment arm will cross over to the next treatment arm (or have their final in-person visit should this occur during the final treatment period).

Participants who experience a treatment failure event that also meets the criteria for an asthma exacerbation, will be treated with Prednisone. For both adults and children, the recommended prednisone dose for acute exacerbations is 2 mg/kg/day (maximum 60 mg) as a single morning dose for three days followed by 1 mg/kg/day (maximum 30 mg) as a single morning dose for 2 days; all administered doses will be rounded down to the nearest 5 mg in children. Participants will be assessed in person and by phone on days 0, 3, 10, 14, and 21. Additional visits and treatment for exacerbations is at the discretion of the treating physician.

E. Rescue Algorithm for Asthma Exacerbations and Treatment Failure Non-responders

Participants who are not responsive to the treatment failure rescue algorithm or those who develop asthma exacerbations will be managed according to the following rescue algorithms. Rescue algorithms are based on recommendations from the NAEPP Guidelines for Diagnosis and Management of Asthma and prior ACRN trials. Albuterol and oral prednisone are the principal medications for rescue management and participants will be instructed in their

use for home management. Oral prednisone will be used if alteration of inhaled corticosteroid does not resolve the exacerbation. For severe acute episodes of asthma, treatment will be administered according to the best medical judgment of the treating physician.

Home Care

Asthma exacerbations will be recognized by criteria described above. Participants will be educated to recognize exacerbations as early as possible to facilitate prompt treatment and to lessen morbidity.

Participants who recognize increased symptoms and/or a fall in PEF to $\leq 65\%$ baseline will use albuterol by MDI, 2-4 puffs, every 20 min up to 60-90 min if needed and then every 4 hours, or less, if needed.

If the PEF does not increase to $>65\%$ baseline or if symptoms are not improved after the first 60-90 min of therapy, the participant should contact the investigator, their primary physician or seek care in the emergency department. Failure of albuterol to control or maintain PEF $>65\%$ baseline may necessitate the use of oral steroids (see below).

Physician's Office or Emergency Room Treatment

Participants will be assessed by history, physical examination, and by physiological monitoring including spirometry or PEF. If the participant's PEF and/or FEV₁ are less than 25% predicted or if the participant shows evidence of altered mental status, cyanosis, labored breathing, or use of accessory muscles,

sampling of arterial blood for respiratory gas analysis is indicated, with appropriate action taken depending on the results obtained.

When treated in the physician's office or the hospital emergency room, participants should initially be given albuterol by nebulization (0.5 cc of 0.5% solution) every 20 min over the first 60-90 min.

If the PEF increases to >65% baseline after the first 60-90 min, the participant can be discharged to continue treatment at home. Prednisone may be administered at the discretion of the physician to augment therapy.

If symptoms persist and PEF remains ≤65% baseline, nebulized albuterol should be continued as often as every 20 min at the discretion of the treating physician. Oral or parenteral corticosteroids should be considered. Monitoring of PEF or spirometry should continue every hour. Within 4 hours of treatment, a decision should be made regarding participant disposition.

If PEF increases to >65% baseline within 4 hours, the participant can be discharged to continue treatment at home. Home treatment should include a 5-day course of prednisone (see below).

If PEF remains >40% but ≤65%, an individualized decision should be made to hospitalize the participant for more aggressive therapy or to continue therapy at home with a course of prednisone.

If PEF is ≤40% baseline after repeated albuterol treatments, the participant should be admitted to the hospital unless in the physician's best judgment alternative treatment could suffice.

Prednisone Treatment

The recommended dose of prednisone used during an acute exacerbation is 2 mg/kg/day (maximum 60 mg) as a single morning dose for three days followed by 1 mg/kg/day (maximum 30 mg) as a single morning dose for 2 days; all administered doses will be rounded down to the nearest 5 mg in children. Participants will be assessed in person and by phone on days 0, 3, 10, 14, and 21. Additional visits and treatment for exacerbations is at the discretion of the treating physician.

XI. PARTICIPATING PARTNERSHIPS

Nine AsthmaNet Clinical Center partnerships (and their associated satellites) will participate in the SIENA study. Each partnership has recruitment and retention plans in place to maximize enrollment. These nine partnerships include:

Brigham and Women's Hospital, Boston, MA

Chicago Metropolitan Asthma Consortium, Chicago, IL

National Jewish Health, Denver, CO

University of Wisconsin, Madison, WI

University of Pittsburgh, Pittsburgh, PA

Washington University, St. Louis, MO

University of California, San Francisco, CA

University of Arizona, Tucson, AZ

Wake Forest University, Winston-Salem, NC

XII. REFERENCES

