Because SIENA invokes a three-way crossover design, a stratified randomization based on prognostic factors is not critical. Instead, we only will invoke clinical site within phenotype (eosinophilic, non-eosinophilic) as a stratifying variable with permuted blocks of size six (one complete cycle of the six sequences). When a participant at a particular Clinical Center is deemed eligible for the study, the Clinic Coordinator will access the AsthmaNet Randomization Module. After entering the participant's pertinent information, the Clinic Coordinator will be asked to verify that all of the entered information is correct. If so, the Clinic Coordinator will be given inhaler numbers to be dispensed to that participant. At certain visits, the coordinator will access the Randomization Module again to generate new inhaler numbers containing the regimen consistent with the participant's randomized drug sequence. In order to maintain security of the randomization schedules, DCC data management and

coordination staff will receive automatically a notice from the AsthmaNet server that a participant has been randomized and/or had a new inhaler number generated.

B. Masking

To minimize the bias due to possible knowledge of the sequence assignment, the study will be double-blinded. Thus, the investigators and the participants will not know which treatments are being administered during the treatment periods.

C. Statistical Analysis Plan for the Primary and Secondary Outcomes

The SIENA trial invokes a three-way crossover design. Each of the three treatment periods endures for 12 weeks, but the data from the first four weeks of each treatment period are not used in the statistical analyses because of the lack of wash-out periods in the crossover design.

The primary outcome in the SIENA trial is a composite based on the three components of treatment failure, asthma control days (ACDs), and FEV₁. For each SIENA participant, we will compare ICS to placebo and LMA to placebo in a hierarchical manner based on the data from the latter eight weeks of their respective treatment periods. The process is described as follows for the generic comparison of treatment regimen A to treatment regimen B:

1. If the SIENA participant does not experience treatment failure on treatment regimen A, but does experience treatment failure on treatment

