4. Application of univariable and multivariable logistic regression that uses sputum eosinophils, blood eosinophils, FENO and serum periostin, as well as bronchodilator reversibility, measures of atopy, and other phenotypic characteristics from both eosinophilic and non-eosinophilic participants to construct ROC curves and c (concordance) statistics to identify “cutpoints” for each biomarker (which also can be compared with previously suggested cutpoints) to examine the value of these biomarkers as predictors of response to treatments.

All of the analyses described above will follow the intention-to-treat paradigm whereby all available data from randomized participants are included in the analyses regardless of information about deviations from study protocol.

D. Statistical Analysis Plan for Additional Secondary Outcomes

We will analyze separately each of three components of the composite outcome as secondary outcomes. We will apply a proportional hazards regression analysis for the time to treatment failure, with a random effect term (frailty) for the SIENA participant to account for the correlations within the SIENA participant ²⁷. The proportional hazards regression model will include fixed terms for treatment regimen, sequence, period, and season of enrollment and an additional random effect term for clinical site. We will apply a linear mixed-effects model for longitudinal data on ACDs and FEV₁. The statistical model will include

(1) fixed effects for treatment regimen, sequence, period, and season of enrollment (spring, summer, fall, winter) nested within each of the eosinophilic and non-eosinophilic phenotypes. (2) a random effect for clinical site within each of the eosinophilic and non-eosinophilic phenotypes, and (3) a 7×7 unstructured variance-covariance matrix for the seven measurements per participant (baseline and two timepoints within each of the three periods). We will apply a similar statistical approach for the other secondary outcomes that are measured on a continuum, such as diary peak flow values and logarithmic-transformed methacholine challenge PC_{20} . We will analyze time to asthma exacerbation in a manner similar to that for time to treatment failure.

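### First-month treatment failures and exacerbations fall outside the by-regimen time-to-event analyses, and the plan gives those analyses no time origin or risk window

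*Combined protocol and SAP*

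**What the plan says.** Section VIII.C states that "Each of the three treatment periods endures for 12 weeks" and that "the data from the first four weeks of each treatment period are not used in the statistical analyses". The reason given is "because of the lack of wash-out periods in the crossover design". Sections I, IV.A, IV.D and VI.A repeat the rule in general terms, as censoring of the first four weeks.

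For the primary outcome the window is explicit. III.H uses the last eight weeks, and VIII.C makes each comparison "based on the data from the latter eight weeks of their respective treatment periods".

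III.I lists asthma exacerbations, time to treatment failure and time to first exacerbation as secondary outcomes, so they come under the heading of VIII.C. Their models are in VIII.D: "We will apply a proportional hazards regression analysis for the time to treatment failure", with a participant frailty, and then "We will analyze time to asthma exacerbation in a manner similar to that for time to treatment failure". Neither sentence says when the clock starts, when a participant enters the risk set, or what happens to an event before week 5.

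Two other parts of the protocol matter here:

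- Under IV.D, VI.D and X.D, an exacerbation or a second treatment failure moves the participant to the next regimen, or to the final visit in period 3. After a single treatment failure the participant takes rescue treatment and stays in the period.
- X.C treats both events as asthma-related adverse events and says that "Safety net procedures, including visits and frequent telephone contacts, are in place to identify participants who experience a treatment failure". VIII.F separately provides semi-annual safety analyses of the three regimens and DSMB monitoring of all safety data.

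**The concern.** Dropping the first month is a sensible guard against carryover for asthma control days, FEV1 and PEF. It suits event outcomes less well, because the events are few and because they change follow-up.

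An exacerbation in weeks 1-4 is not analysed. It also triggers crossover, so that participant adds essentially no weeks 5-12 time on that regimen. The weeks 5-12 comparison is then restricted to people who got through the first month, and the regimen itself helps decide who they are. If early failures are more frequent on regimens without an inhaled corticosteroid, the reported event results would understate them. IX.B expects deterioration in a significant number of participants, and the trial asks whether non-eosinophilic patients need a different treatment strategy, so these are results that readers will look for.

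A single early treatment failure raises a different problem. The participant stays in the period, but the plan does not say whether a later failure then counts as the first.

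**Working it through.** The plan gives no rate or timing for treatment failure or exacerbation, so there is no stated figure to reproduce. Only the time fraction comes from the documents.

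**Inputs.** Period length is 12 weeks and the excluded window is 4 weeks (both VIII.C). Randomized total is 336 (VIII.A). Event risk per period, q, and the shape of the hazard are assumptions.

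**Step 1: excluded time.** 4/12 = 33.3% of scheduled time per period.

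**Step 2: share of first events, constant hazard.** With L = -ln(1 - q)/12, the share in weeks 1-4 is (1 - exp(-4L))/q. The counts assume 336 participants on a regimen and no drop-out.

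| Assumed 12-week risk q | Share in weeks 1-4 | Events on one regimen | Of these, in weeks 1-4 |
|---|---|---|---|
| 5% | 33.9% | 16.8 | 5.7 |
| 10% | 34.5% | 33.6 | 11.6 |
| 20% | 35.8% | 67.2 | 24.1 |

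At higher risks the share rises, to 37% at 30% and 41% at 50%.

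**Step 3: share when the hazard is not constant.** If the weekly hazard in weeks 1-4 is h times the later one and events are rare, the share is 4h/(4h + 8).

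- h = 0.25: 1/9 = 11%
- h = 0.5: 2/10 = 20%
- h = 1: 4/12 = 33%
- h = 1.5: 6/14 = 43%
- h = 2: 8/16 = 50%

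The shape of the hazard therefore matters much more than the event rate.

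**Step 4: what VIII.D leaves open.** At q = 10% with constant hazard, a model from day 1 has 33.6 first events on a regimen. A model confined to weeks 5-12 has 33.6 - 11.6 = 22.0. For treatment failure there is a further choice: someone with one failure in week 2 and another in week 8 could be left out as already failed, or entered at week 5 as event-free. VIII.D permits either.

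**Step 5: selection.** At 10% risk, 11.6/336 = 3.5% of participants have a first event in weeks 1-4; at 5% risk, 5.7/336 = 1.7%. For exacerbations these people leave the risk set. At such rates the depletion is small. It distorts the hazard ratio only if the regimen effect differs between the first month and later, or if those who leave are at higher underlying risk. The loss of events is the larger and more certain effect.

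**The case against.** The strongest case on the other side is that the exclusion is deliberate. Without a washout, an early event in period 2 or 3 may belong to the previous regimen. An inhaled corticosteroid period followed by placebo could suppress early placebo events, and that too would understate the harm of having no corticosteroid. Rescue treatment adds to this: the crossover visit after an exacerbation falls about three days into a five-day prednisone course (VI.D, X.C), so the next regimen starts under systemic steroid. Assigning events by onset date does not remove that protected time. This stands, and it is why a day-1 analysis belongs beside the weeks 5-12 analysis and should not replace it. It has less force in period 1, which follows a placebo run-in with no earlier randomized drug.

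Three stronger inferences are tempting, and the documents do not support them.

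- A reader might infer that early events disappear from safety reporting. The four-week rule sits in the plan for primary and secondary outcomes and rests on a crossover argument. VIII.F stands apart and keeps all safety data under DSMB review. The narrower gap is that no final by-regimen safety summary is described.
- A reader might infer that VIII.C contradicts itself by also saying that "all available data from randomized participants are included in the analyses regardless of information about deviations from study protocol". That sentence defines intention-to-treat. A prespecified window is not a protocol deviation, and the sentence refers to the analyses above it, whereas the event models follow in VIII.D.
- A reader might take a third as the proportion of events lost. It is the proportion of time; as a proportion of events it assumes a roughly constant hazard.

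No power loss is claimed here. A figure would need an assumed hazard ratio that is equal in and after the first month, and carryover could weaken the early contrast.

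**Conclusion.** The point holds for the secondary event analyses. As written, treatment failures and exacerbations in weeks 1-4 of each period are outside the by-regimen time-to-event results, and VIII.D does not define origin, entry or the status of an earlier event. The documented size is 4 of 12 scheduled weeks. As a share of first events it is 34% to 36% under constant hazard with 5% to 20% risk per period, or 11% to 50% with early-to-late hazard ratios of 0.25 to 2; both ranges rest on assumed rates. The selection on getting through the first month is real for exacerbations and second treatment failures. It does not apply to a single treatment failure, which leaves the participant in the period. Neither the primary preference analysis nor DSMB oversight is in question here.

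**What to change.** 1. In VIII.C, state that the weeks 5-12 window applies to the primary hierarchy and to the asthma control day, FEV1 and PEF analyses.
2. In VIII.D, state the time origin, risk window and entry rule for time to treatment failure and time to exacerbation, and say whether a failure after week 4 counts as the first when one occurred earlier in the same period.
3. Keep the weeks 5-12 event analysis and prespecify a full-period analysis beside it: treatment failures and exacerbations by regimen over all time on that regimen, with counts, rates per person-time and a time-to-event model from day 1. Assign each event by onset date. Person-time is the right denominator because periods can be cut short or extended after events.
4. Add a period-1-only version, where no earlier randomized drug can carry over.
5. State that the final by-regimen summaries of adverse and serious adverse events use all on-treatment time.

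No clinical rule changes and no new data are needed, since the events are already captured at visits, at phone calls and in the diary. The cost is SAP wording and one extra set of tables. The full-period results in periods 2 and 3 may include carryover from the previous drug and from rescue steroids around the crossover, and the report should say so. The period-1 version is free of randomized-drug carryover but has only about a third of the participants on each regimen.
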